2.3 Endpoints

2.3.1 Primary endpoints:

- 2.3.1.1 Feasibility: Successful completion of treatment including use of perfusion MR in plan optimization.
- 2.3.1.2 Safety: Rate of liver decompensation (change in Child-Pugh score >2 and ALBI score > 0.5) and grade 3 GI bleeding. The former are lab values that are already collected as standard of care. The latter will be assessed via the NCI CTCAE version 4.0.
- 2.3.1.3 Efficacy: Lesion-specific local control

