5.5 Duration of Follow-Up

Patients will be followed for 2 years after completion of treatment or until death, whichever occurs first. If patients progress outside of the treated tumor, they will only be followed for survival, without mandated visits with study personnel, as long as they are being seen routinely every 3-6 months by an oncologist or hepatologist. These clinic notes can be requested for study purposes, and tumor measurements tracked from clinical scans.

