5.6 Off Study Criteria

Patients can be taken off study at any time at their own request, or they may be withdrawn at the discretion of the investigator for safety, behavioral or administrative reasons. Patients will be considered off study after completion of protocol treatment and follow-up criteria.

The reason(s) for discontinuation from study will be documented and may include:

5.6.1 For patients planning to receive ICG testing in lieu of ALBI, patients will be removed if

- they are unable to complete the pre-treatment and post- 3 fraction IC Green tests, as these are necessary for dose adjustment.
- 5.6.2 Patients will be removed if they are unable to receive RT treatments.
- 5.6.3 Patients may be removed from study at any time by patient request.
- 5.6.4 Patients who enroll in subsequent liver radiation therapeutic trials are considered off study for initial enrollment. Local control for all treated lesions will be tracked on the follow up schedule for the subsequent enrollment to avoid duplicate procedures.
- 5.6.5 Patients who have progression of the treated lesion will be followed for survival and toxicity only.
- 5.6.6 Patients who go on to receive additional liver-directed to the treated lesion or systemic therapy (non-radiation therapy, on or off protocol) will be followed for survival only.
- 5.6.7 Patients can be removed from study if they are unable to comply with protocol requirements.
- 5.6.8 Patients can be removed from study if the treating physician judges that continuation on the study would not be in their best interest.

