6.0 STUDY PROCEDURES

6.1 Screening/Baseline Procedures

Assessments performed exclusively to determine eligibility for this study will be done only after obtaining informed consent. Assessments performed for clinical indications (not exclusively to determine study eligibility) may be used for baseline values even if the studies were done before informed consent was obtained.

All screening procedures must be performed within 30 days prior to registration unless otherwise stated. Baseline procedures to be completed prior to radiotherapy. The screening procedures include:

- 6.1.1 Informed Consent
- 6.1.2 Medical history
- 6.1.3 Review subject eligibility criteria
- 6.1.4 Physical exam: To include ascites and encephalopathy
- 6.1.5 Performance status
- 6.1.6 Baseline adverse event assessment
- 6.1.7 Hematology: CBC
- 6.1.8 Serum chemistries: Comprehensive metabolic panel (CMP) to include: albumin, alkaline phosphatase, ALT, AST, BUN, creatinine, electrolytes (sodium, potassium), glucose, and total bilirubin.
- 6.1.9 Coagulation assessment: PT/INR
- 6.1.10 Tumor assessment: The longest dimension of each tumor to be treated will be measured and recorded either on the most recent diagnostic scan or simulation scan.
- 6.1.11 Indocyanine green or ALBI baseline testing: ICG retention or ALBI will be measured by blood test after study enrollment and prior to radiotherapy.
- 6.1.12 Blood draw for correlative studies after study enrollment and prior to radiotherapy. See Section 10.0 for details.
- 6.1.13 For patients who consent to this portion of the study, tumor biopsy will also be performed (see section 10.1.2) after study enrollment and prior to radiotherapy.

Generally, this would be performed at the time of clinically necessary fiducial placement for radiation targeting.

6.1.14 Quality of life assessment after study enrollment and prior to radiotherapy: FACT-HEP (Version 4).

6.2 Procedures During Treatment: See section 5

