7.0 MEASUREMENT OF EFFECT

7.1 Antitumor Effect- Solid Tumors

Response and progression will be evaluated in this study using criteria similar to the international criteria set by the Response Evaluation Criteria in Solid Tumors (RECIST) Committee [JNCI 92(3):205-216, 2000]. However, rather than tracking the sum of longest diameters, *each treated tumor will be assessed individually* and the longest diameter tracked in these lesion-specific tumor measurements. Additionally, at least 4mm change is required for a lesion to be deemed to have progressed or responded. mRECIST will also be tracked where possible.³⁰

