7.1.2 Disease Parameters

All tumor measurements must be recorded in millimeters. The same method assessment and the same technique should be used to characterize each identified and reported lesion at baseline and during follow-up if at all possible.

Target lesions. All tumors treated with radiotherapy are considered *target lesions* and measured and recorded separately at baseline and during follow up scans.

Non-target lesions. All other tumors are considered *non-target lesions* and will not be tracked except when noted as new or progressive (either within the liver or outside of the liver) on followup scans. Measurements are not required.

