11.3 Data Analysis Plans

Primary Aims: The first primary aim is feasibility which is defined as the ability to successfully deliver the full treatment including all adaptations and in particular the perfusion based planning and replanning. In the simplest analyses, feasibility will simply be summarized as the proportion of patients for whom the intended treatment was feasible. The reasons for lack of feasibility for any patients will be investigated individually.

The primary efficacy endpoint is local control, measured as the time to progression of the treated lesion. Patients with no evidence of local progression at the time of data analysis will be censored at the last date on which they were evaluated for local progression. Local progression will be summarized with Kaplan-Meier curves. The estimated rate of local control at 6, 12, 18 and 24 months will be estimated and reported with 95% confidence intervals. Cox regression models will be used to assess the relation between the hazard of local progression and tumor dose and other covariates.

The primary toxicity endpoint is defined as a change in Child Pugh score of greater than or equal to 2 within 6 months of SBRT. Secondary toxicity endpoints include changes in ALBI scores and grade 3 toxicities described in section 8. RILD is a rare but serious side effect that will also be summarized if it occurs. Logistic regression models will be used to estimate the association between baseline (primarily baseline liver function such as CP score and mean liver dose and other dose metrics such as D700) and mid-treatment variables (e.g. change in ICGR15) and the probability of toxicity. We will include interactions between dose and baseline liver function as there is some evidence that patients with worse liver function are more sensitive to radiation than patients with better baseline liver function.

Secondary Aims: The relation between various biomarkers and treatment efficacy will be assessed by including the biomarkers as covariates in Cox regression models for local progression. The relation between biomarkers and toxicity will be assessed in logistic regression models for the binary or ordinal toxicity outcomes and linear regression models for continuous measures of toxicity or liver function such as ICGR15 or ALBI.

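### Section 5.6.5, read literally, ends tumor assessment for the whole patient when the treated lesion progresses, so a per-lesion local control estimate may be biased upward in patients with several treated lesions

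*Combined protocol and SAP*

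**What the plan says.** - **Endpoint.** Section 2.3.1.3 makes the primary efficacy endpoint "Lesion-specific local control".
- **Unit of assessment.** Under section 7.1, "each treated tumor will be assessed individually". Section 7.1.2 makes all irradiated tumors target lesions, "measured and recorded separately at baseline and during follow up scans".
- **Several lesions per patient are possible.** Section 6.1.10: "The longest dimension of each tumor to be treated will be measured and recorded". No section gives the number or share of patients expected to have more than one.
- **Follow-up after local failure.** Section 5.6.5: "Patients who have progression of the treated lesion will be followed for survival and toxicity only". It does not mention other treated lesions in the same patient.
- **Neighboring rules.** After progression outside the treated tumor, section 5.5 allows "tumor measurements tracked from clinical scans". Section 5.6.4 keeps all treated lesions under local-control tracking when a patient joins a later liver radiation trial. Section 5.6.6 reduces follow-up to survival alone after further liver-directed therapy to the treated lesion or systemic therapy.
- **Analysis.** Section 11.3 measures time to progression of the treated lesion, in the singular. Patients without local progression are "censored at the last date on which they were evaluated for local progression". Kaplan-Meier rates are reported at 6, 12, 18 and 24 months, and a Cox model relates local progression to tumor dose.
- **Decision rule.** Section 11.2 requires 1-year local control of at least 80% to move to a phase II trial.

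**The concern.** The endpoint is defined per lesion, but the rule that ends tumor follow-up acts on the patient. Suppose two tumors are treated and one progresses at 6 months. As 5.6.5 is written, nobody is asked to measure the other again, and a lesion-level analysis censors it at about 6 months.

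Kaplan-Meier assumes that censored lesions have the same later risk as those still followed. Lesions in one patient share tumor biology and the same liver-driven limits on dose, so a lesion whose sibling has just failed may well be at higher risk. Censoring it then removes above-average risk from the risk set, and estimated control rises.

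Three things are at stake: the comparison with the 80% criterion, the 18- and 24-month rates, and the dose-control Cox model. That model feeds second-course dose selection (11.1), and section 11.2 already expects few local progression events for it. A cluster-robust variance would repair the standard errors but not the missing failures, and measurements never recorded cannot be recovered at analysis.

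**Working it through.** **1. The plan's own figures.** The plan gives no figure for this bias. The nearest is the efficacy stopping rule in 8.7, 5 or more of 10 patients. The exact binomial tail P(X ≥ 5 | n = 10) is 0.2%, 15.0% and 62.3% at true rates of 10, 30 and 50%, against the stated 1, 15 and 62%. The rule reproduces, with the patient as its unit.

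**2. When the bias is zero.** It vanishes if each patient has one treated lesion, if lesion failures within a patient are independent, or if the analysis is per-patient time to first treated-lesion progression.

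**3. Direction, in closed form.** Take a shared gamma frailty with parameter θ (Kendall's tau = θ/(θ+2)), every patient with m lesions, and cumulative baseline hazard L. True lesion control is (1 + θL)^(−1/θ). With siblings censored at the first failure, the Kaplan-Meier limit is (1 + mθL)^(−1/(mθ)), which is larger whenever θ > 0 and m > 1.

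For true control 0.80 and tau 0.5 (θ = 2), L = (0.80^(−2) − 1)/2 = 0.281.
- m = 2: (1 + 4 × 0.281)^(−1/4) = 0.828.
- m = 3: (1 + 6 × 0.281)^(−1/6) = 0.848.

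These are near-worst cases: all patients multi-lesion and assessment continuous. With 3-monthly scans, simulation gives 82.1% and 83.5%, because siblings failing by the same scan both count as events.

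**4. Size in mixed populations.** Assumptions: exponential lesion times, Gaussian copula with correlation 0.3 to 0.8, progression found on a 3-monthly grid (6.3 says about every 3-6 months), no deaths or dropout. Upward bias in percentage points, from a true 80% at 1 year and 0.80² = 64% at 2 years:

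| Patients with two lesions | 1 year | 2 years |
|---|---|---|
| 10% | 0.1 to 0.6 | 0.4 to 1.2 |
| 30% | 0.5 to 1.5 | 1.1 to 3.2 |
| 60% | 0.8 to 2.5 | 2.0 to 5.4 |

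With three lesions in 30-60% of patients, the estimates are about 81-84% at 1 year and 66-73% at 2 years. The gamma frailty model, with two lesions in 20-40% of patients and tau 0.2 to 0.8, gives 0.2 to 2.0 points at 1 year and 0.6 to 3.3 at 2 years.

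**5. Size at the control the protocol expects.** Section 5.1.2.3 cites 95% at 2 years; under a constant hazard that is √0.95 = 97.5% at 1 year. Section 1.1.2.3 reports 97% at 1 year in the preceding study. From 97.5%/95%, with two lesions in up to 60% of patients, the bias is at most about 0.3 point at 1 year and 0.7 at 2 years. From 95% at 1 year, the frailty model with 20-40% multi-lesion gives about 0.4 point or less at 1 year.

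**6. Scale.** The binomial standard error of 80% with n = 80 is √(0.8 × 0.2/80) = 4.5 points. Close to the criterion, with tau 0.5 and near-continuous assessment, a true 79% (20% of patients with two lesions) or 78% (40%) is estimated as about 80%.

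**7. The unit itself matters more.** With tau 0.5, two lesions in 40% of patients and 3-monthly scans, a lesion-level 80% at 1 year corresponds to a patient-level 75.5% free of any treated-lesion progression.

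**The case against.** A reader might infer that 5.6.5 cuts off tumor follow-up once any treated lesion progresses, and that reported local control therefore is overstated. The documents do not support that stronger reading, for three reasons.

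- **Wording of 5.6.5.** It speaks of one treated lesion and does not address a patient with one failed and one controlled tumor. Applying it to siblings is an inference, and 7.1.2 points the other way by requiring every target lesion to be measured on follow-up scans.
- **Unit in 11.3.** Censoring is worded for patients, 7.1.4 defines control over all treated tumors together, and the 8.7 rule counts patients. If the analysis is time to first treated-lesion progression, the first failure is the event and nothing is overstated. Lesion-specific could mean only that remote progression does not count.
- **Size.** It rests on a multi-lesion share and a correlation that the documents do not give. In every two-lesion scenario in the table, the 1-year bias is not much more than half a standard error, and this is a pilot seeking preliminary estimates.

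All three stand as limits on the claim. They do not remove it. Nothing in the text says that siblings stay under assessment after a local failure, although 5.5 and 5.6.4 say so for other situations. The per-patient reading of 11.3 sits badly with the endpoint in 2.3.1.3. Either way the sections need reconciling.

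It is also fair to object that changing 5.6.5 alone would not be enough: a patient who receives further therapy after local failure would lose sibling follow-up under 5.6.6.

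**Conclusion.** The point holds conditionally. As written, 5.6.5 leaves sibling lesions without assessment after a local failure. If local control is analysed per lesion, as 2.3.1.3 implies, the 11.3 censoring is then informative and can only push the estimate upward when within-patient correlation is positive. For true 1-year control of 80% and two lesions in 10-60% of patients, the bias is about 0.1-2.5 points at 1 year and 0.4-5 points at 2 years. Near 97.5%, it is about 0.4 point or less at 1 year. It is none under a per-patient first-progression analysis.

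The figures rest on assumed multi-lesion shares, correlations and 3-monthly scans, and ignore death and other dropout. Longer scan intervals would shrink the bias; three lesions per patient would enlarge it. This is a cheap improvement worth making because it protects the primary endpoint near its 80% criterion. It is not evidence that the trial's local control will be materially wrong.

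**What to change.** 1. **Section 5.6.5.** State that only the progressed lesion leaves local-control follow-up. The patient is followed for survival and toxicity, and all other treated lesions continue to be measured on routine clinical scans, using the provision already in 5.5, until their own progression, death or 2 years.
2. **Section 5.6.6.** Make the same data-collection provision, and flag readings taken after new liver-directed or systemic therapy so that the analysis can examine results with and without them.
3. **Section 11.3.** State that the unit of analysis for local control is the lesion, to match 2.3.1.3, word the censoring rule for lesions, and use a cluster-robust variance for the confidence intervals and the Cox model. If the sponsor prefers the patient as the unit, 2.3.1.3 should be reworded instead and the event defined as first progression of any treated lesion.

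Cost: a few sentences in three sections and some extra measurements on scans already being done, with no added imaging or visits. The downside is that some later readings will be confounded by subsequent therapy, which is why they should be flagged.

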5.7 Patient Replacement

Patients who do not complete the pre-treatment and post 3/5 of treatment IC Green tests or bloodwork to evaluate ALBI score, along with the initial 3/5 of treatment are considered non-evaluable and will be replaced until a total of 80 evaluable patients is reached (80 patients).

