11.2 Sample Size and Accrual

This is a pilot trial to gather the data necessary to plan a randomized phase II study with a control group receiving standard therapy. The planned accrual is 80 evaluable patients over two years. An evaluable patient is a patient that has received their complete prescribed treatment (including those whose ICG measurements or ALBI precluded the second phase of treatment and those for whom other toxicity prevented them from receiving a full course of treatment). The high level goal of this trial is to define an individualized and adaptive approach to use of RT in this patient population. Key components of individualizing and adapting treatment are models that relate expected toxicity and tumor control outcomes to RT dose and other patient level characteristics. Part of the reason for the sample size of 80 is to refine these models prior to initiating a randomized trial. For toxicity, our preliminary data suggests that mean liver dose (or some other measure of dose to normal liver), baseline liver function (e.g. CP score) and mid-treatment change in ICGR15 are the most important factors. If our overall event rate for toxicity is about 20%, we expect to have approximately 16 toxicity events which, in combination with some data from similarly treated previous patients, should be sufficient to estimate parameters in a toxicity model with 3 predictors. For tumor control, tumor dose is expected to be the most significant predictor. There will likely be a lower rate of local progression events so that this model may need to have fewer predictors. In addition to further defining statistical models this trial will permit us to estimate rates of toxicity and tumor control that will be key when designing a randomized trial with power to reject a specific null hypothesis.

This treatment will be considered sufficiently promising to initiate a phase II trial if it causes toxicity (increase in CP score of 2 points or more within 6 months of treatment) in no more

than 25% of patients and results in a local control rate (at 1 year) of at least 80%.

We expect to be able to accrue 20 patients per year and thus to complete accrual in approximately 4 years.

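### Section 5.7 replaces some patients who are feasibility failures, and 11.3 names no denominator; if it is the 80 evaluable patients, feasibility is overstated by 1/(1−d), where d is the share of enrolled patients replaced

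*Combined protocol and SAP*

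**What the plan says.** Section 2.1 lists feasibility as the first primary objective. Section 2.3.1.1 defines the endpoint as "Successful completion of treatment including use of perfusion MR in plan optimization". Section 11.3 describes it as "the ability to successfully deliver the full treatment including all adaptations", with emphasis on planning and replanning from perfusion MRI. It gives the statistic in one line: "feasibility will simply be summarized as the proportion of patients for whom the intended treatment was feasible". It adds that reasons for failure will be looked into patient by patient. It does not say whether the denominator is enrolled, treated or evaluable patients.

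Section 5.7 deals with patients who lack the baseline and mid-course ICG tests or ALBI bloodwork. These patients, "along with the initial 3/5 of treatment are considered non-evaluable and will be replaced until a total of 80 evaluable patients is reached". Section 5.6.1 takes patients assigned to ICG off study if "they are unable to complete the pre-treatment and post- 3 fraction IC Green tests, as these are necessary for dose adjustment", and 5.6.2 does the same for patients who cannot receive RT.

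Section 11.2 has its own definition: "An evaluable patient is a patient that has received their complete prescribed treatment". It then keeps two groups as evaluable: patients whose ICG or ALBI result ruled out the second phase, and "those for whom other toxicity prevented them from receiving a full course of treatment".

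Analysis sets are stated for toxicity and response (7.1.1) and for safety (7.2). None is stated for feasibility.

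**The concern.** A patient who cannot complete the first three fifths of RT, or who has no mid-course liver function result, has not received a full course with its adaptations. On the plan's own definition that is a failure of the first primary endpoint. Section 5.7 labels the same patient non-evaluable and enrols a substitute. The only final population given a size is the 80 evaluable patients (synopsis, 5.7, 11.2), so an analyst who finds no denominator in 11.3 will naturally use them. Those failures then drop out of both numerator and denominator.

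Two analysts could therefore report different primary results from the same data, and the more natural choice gives the more favourable one. The pilot is meant to prepare a randomized comparison, and its completion rate would be read as evidence that the strategy can be delivered.

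The success criterion is also open. A patient given no second phase because the protocol's own rules so direct (liver function in 5.3 and 11.1, or no remaining enhancement in 11.1) has not had the full planned course. Yet the strategy was carried out as designed. Section 11.3 does not say how that patient counts.

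**Working it through.** **The plan's own figure.** The only quantity that the documents derive from the 80 is the expected number of toxicity events in 11.2: 80 × 0.20 = 16, as stated. This confirms that arithmetic but does not bear on feasibility. No feasibility rate, feasibility threshold, replacement rate or total enrolment is given.

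**Inputs.** From the documents: 80 evaluable patients, with replacement until that number is reached. Assumed:
- d, the share of enrolled patients replaced: 5%, 10% or 20%
- r, the feasibility failures that remain among the 80: 8 in the main example, with other values below

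Section 5.7 is read as making a patient non-evaluable if any one of the listed elements is missing. If all had to be missing, d would be smaller.

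**Formulas.**
- Enrolled: N = 80/(1−d), rounded up. Replaced: k = N − 80.
- Rate in the evaluable set: (80−r)/80. Rate over all enrolled: (80−r)/N.
- Ratio of the two: N/80, which is 1/(1−d) before rounding.

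**Results with r = 8** (Clopper-Pearson 95% intervals). The evaluable-set rate is 72/80 = 90.0% (81.2 to 95.6) in every row.

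| d | N | k | Over all enrolled | 1/(1−d) |
|---|---|---|---|---|
| 5% | 85 | 5 | 72/85 = 84.7% (75.3 to 91.6) | 1.05 |
| 10% | 89 | 9 | 72/89 = 80.9% (71.2 to 88.5) | 1.11 |
| 20% | 100 | 20 | 72/100 = 72.0% (62.1 to 80.5) | 1.25 |

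Rounding up to whole patients makes the realised ratio N/80 slightly larger in the first row (85/80 = 1.06). At 10% replaced, the all-enrolled estimate of 80.9% already lies just below the interval that would be reported around 90%.

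**Share of all failures that replacement removes**, k/(k+r), at 10% replaced (k = 9):
- r = 4: 9/13 = 69%
- r = 8: 9/17 = 53%
- r = 16: 9/25 = 36%
- r = 24: 9/33 = 27%

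Replacement removes more than half of the failures only if k exceeds r. That means r of 8 or fewer at 10% replaced, and r of 4 or fewer at 5% replaced.

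**The two definitions side by side.**

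| Patient | 5.7 | 11.2 |
|---|---|---|
| Toxicity stops RT before three fifths | Non-evaluable, replaced | Evaluable |
| Completes three fifths and both tests, then withdraws | Evaluable | Not evaluable |
| Perfusion MRI not used in planning or replanning, all else done | Evaluable | Evaluable |

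The first two rows contradict each other. The third shows that neither definition screens out the component that 11.3 singles out.

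**The case against.** The strongest reply is that 11.3 never says feasibility is computed in the 80. Sections 5.7 and 11.2 set an accrual target, and 11.3 promises to look into failure in any patient. That is correct: use of the 80 is an inference. However, nothing in 11.3 places replaced patients in the denominator, and investigating reasons one by one does not change a proportion.

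A reader might infer that most failures are removed, or that the rate must come out close to 100%. The documents do not support either reading. Failures of perfusion-MRI planning or replanning stay in the set under both definitions. An intended but undelivered final two fifths stays under 5.7. Courses cut short by toxicity stay under 11.2. How many of each there will be is not stated.

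A reader might also infer that an inflated rate would trigger the next trial. The criterion in 11.2 for going on is toxicity in no more than 25% of patients and 1-year local control of at least 80%. Feasibility is not part of it and has no threshold anywhere. The harm is therefore to the primary endpoint itself and to what planners of the randomized trial would take from it, not to a formal decision rule.

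Finally, a patient who enrols and never starts RT may say little about whether the adaptive strategy can be delivered. That is fair, and it is why a second figure over treated patients is useful.

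**Conclusion.** The point holds in this form: a replacement rule removes patients who fail the first primary endpoint, and the analysis section does not name a denominator that would bring them back. If the 80 evaluable patients are used, feasibility is overstated by 1/(1−d), a factor of 1.05 to 1.25 for 5% to 20% replaced. With 8 retained failures, that is 90% reported against 85% to 72% of all enrolled. The size rests on three assumptions: that the 80 are the denominator, the replacement share, and the number of retained failures. The conflict between 5.7 and 11.2 over who is evaluable, and the missing rule for a protocol-directed stop after the first phase, need no assumption: both can be read directly from the text.

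**What to change.** - In 11.3, name all enrolled patients as the feasibility denominator, and give a second figure over all who received at least one fraction.
- Count as failures, with reasons, patients replaced under 5.7 or removed under 5.6 before the adaptive course was completed. Do not count patients removed later, during follow-up: 5.6.7, for example, can apply to someone whose treatment was fully delivered.
- State that a protocol-directed omission of the final phase, with the mid-course assessments done, counts as the strategy delivered.
- Reconcile the definitions of evaluable in 5.7 and 11.2, so that the two conflicting patient types above are classified the same way in both.
- Keep the 80 evaluable patients as the set for the dose-outcome models.

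The cost is wording in 5.7, 11.2 and 11.3. No extra patients are needed, and 5.6 already requires reasons for discontinuation to be documented. The downside is that the reported feasibility rate will be somewhat lower.
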